15.8 Premature Discontinuation of the Study

The Sponsor reserves the right to discontinue the study because of safety concerns, ethical issues, or serious and/or persistent noncompliance with the Protocol.

If the study is suspended or terminated, the Sponsor will promptly inform the Investigator and will also inform the regulatory authorities of the suspension or termination of the study and the reason(s) for the action. The Investigator is responsible for promptly informing the IRB and providing the reason(s) for the suspension or termination of the study.

For all subjects, the Follow-up Visit assessments should be performed per Table 2.

In addition, all general Investigator site activities required for the scheduled EOS and site closure should be completed as described in Section 15.7.

The Sponsor may at any time, at its sole discretion, discontinue the study site for various reasons, including, without limitation, the following:

- Failure of the Investigator to enroll subjects into the study at a reasonable rate
- Failure of the Investigator to comply with applicable laws and/or pertinent regulations
- Submission of knowingly false information from the research facility to the Sponsor, Study Monitor, or regulatory authorities
- Insufficient adherence to Protocol requirements

The Sponsor will issue a written notice to the Investigator, which will contain the reasons for taking such action. If the Investigator site is terminated for noncompliance, appropriate regulatory authorities will also be notified by the Sponsor.

15.9 Liability and Insurance

Please refer to the written study information given to the subject.

16 DISCLOSURE OF DATA

16.1 Confidentiality

A Subject Screening and Enrolment Log will be completed at each Investigator site for all subjects who signed an ICF. A Subject Identification Log, documenting the subjects' names, will be completed and retained at each Investigator site for all subjects enrolled in the study.

Subject names will remain confidential and will not be included in the database supplied to the Sponsor or its designee. If the subject name appears on any document collected, eg, hospital discharge summary, the name must be obliterated before the document is transmitted to the Sponsor or its designee. All study findings will be stored in electronic databases. The subjects will give explicit permission for representatives of the Sponsor, regulatory authorities, and the IRB to inspect their medical records to verify the information collected. Subjects will be informed that all personal information made available for inspection will be handled in the strictest confidence and in accordance with laws and regulations. All personnel involved in the study will observe and work within the confines of local data protection regulations.

All information concerning the product as well as any information such as clinical indications for the IMP, its formula, methods of manufacture and other scientific data relating to it, that have been provided by the Sponsor or designee, are confidential and is the sole property of the Sponsor. The Investigator will agree to use the information only for the purposes of carrying out this study and for no other purpose unless prior written permission from the Sponsor is obtained. The Sponsor has full ownership of the eCRFs completed as part of the study.

16.2 Publication

By signing the study Protocol, the Investigator agrees that the results of the study may be used for the purposes of national and international registration, publication, and information for medical and pharmaceutical professionals by the Sponsor. If necessary, the regulatory authorities will be notified of the Investigator's name, address, qualifications and extent of involvement.

The Sponsor will retain ownership of all data. All proposed publications based on the study will be subject to the Sponsor's approval requirements.

The Sponsor or designee will prepare a final report on the study. The Investigator's right to publish or present any information on the study, and publication procedures to be followed, will be defined in the Investigator site agreement.

# **ABBREVIATIONS**

Abbreviations	Definitions
AE	adverse event
AESI	adverse events of special interest
ANCOVA	Analysis of covariance
CRF	case report form
BL	Baseline
BMI	Body mass index
DMC	data monitoring committee
ECG	electrocardiogram
EOS	end of study
EOT	end of treatment
GCP	Good clinical practice
HDL	High-density lipoprotein
ICH	International council for clinical harmonization
ISA	interim safety assessment
ITT	intent-to-treat
LS Mean	Least square mean
MedDRA	medical dictionary for regulatory activities
MMRM	Mixed effect model repeated measure
PK	pharmacokinetics
PP	per protocol
PT	preferred term
RAND	randomized
SAF	safety
SAP	statistical analysis plan
SD	standard deviation
SE	Standard error
SOC	system organ class
TEAE	treatment emergent adverse event
ULN	Upper limit of normality
WHO	World health organization

### 1. INTRODUCTION

This statistical analysis plan (SAP) is based on the protocol amendment 4 dated 04 Mar. 2020. The plan covers statistical analysis, tabulations and listings of the study.

Any statistical analysis details described in this document supersede any description of statistical analysis in the protocol.

# 2. STUDY OBJECTIVE AND ENDPOINTS

Overall, the objective of the study is to evaluate the safety and efficacy of MT-2990 in patients with surgically diagnosed endometriosis, experiencing moderate to severe endometriosis related pain and impact on quality of life. In addition, the study will assess the effects of MT-

# 2.1. Study Objectives

# 2.1.1. Primary Objective

• To assess the efficacy of MT-2990 on the nonmenstrual pelvic pain in women with endometriosis

# 2.1.2. Secondary Objectives

- To assess the efficacy of MT-2990 on the dysmenorrhea in women with endometriosis
- To assess the effect of MT-2990 on the dyspareunia
- To assess the safety and tolerability of MT-2990

# 2.2. Study Endpoints

# 2.2.1. Primary Endpoint

Mean change from Baseline through Week 16 in nonmenstrual pelvic pain

# 2.2.2. Key Secondary Efficacy Endpoint

Mean change from Baseline through Week 16 in dysmenorrhea 2.2.3. Secondary Efficacy Endpoints Mean change from Baseline through Week 16 in dyspareunia score Mean change from Baseline through Week 16 in nonmenstrual pelvic pain Mean change from Baseline through Week 16 in dysmenorrhea Mean change from Baseline through Week 16 in dyspareunia score Mean change from Baseline through Week 16 in pill count of any rescue analgesic use Mean change from Baseline through Week 16 in opioid pill count Time to rescue medications Percentage of nonmenstrual pelvic pain responders through Week 16 Percentage of dysmenorrhea responders through Week 16 Percentage of dyspareunia responders through Week 16 Mean percentage change from Baseline through Week 16 in nonmenstrual pelvic pain Mean percentage change from Baseline through Week 16 in dysmenorrhea Mean percentage change from Baseline through Week 16 in dyspareunia Percentage of nonmenstrual pelvic pain responders through Week 16 Percentage of dysmenorrhea responders through Week 16 Percentage of dysmenorrhea responders through Week 16 Mean percentage change from Baseline through Week 16 in nonmenstrual pelvic pain Mean percentage change from Baseline through Week 16 in dysmenorrhea Mean percentage change from Baseline through Week 16 in dyspareunia Number and percentage of women who responded Mean change from Baseline through Week 16 on Number and percentage of women who responded "

# 2.2.4. Safety Assessments

- Physical examination (including breast examination)
- Vital signs (blood pressure, pulse rate, and tympanic body temperature)
- Electrocardiogram (ECG) parameters (including cardiac intervals: heart rate, PR, QRS, QT, QTcF and QTcB)
- Clinical laboratory assessments (hematology, biochemistry, coagulation, and urinalysis)
- Treatment emergent adverse events (TEAEs)

### 3. STUDY DESIGN

# 3.1. Study Design

This is a Phase 2, randomized, double-blind, placebo-controlled study, stratified by moderate or severe pain to evaluate safety and efficacy of MT-2990 in women with endometriosis-associated moderate to severe pain.

Following the Screening period, eligible subjects who have met all the eligibility criteria and have moderate or severe nonmenstrual pelvic pain, and dysmenorrhea will be randomized into the study. Approximately 38 subjects per arm will be enrolled. Subjects will be randomly allocated to 1 of 2 treatment groups (placebo or MT-2990) in a ratio of 1:1. A single

dose of placebo or

End-of-treatment (EOT) will occur at Week 12 (Visit 7) and primary and secondary efficacy endpoints will be assessed at the Week 16 (Visit 9) visit. Subjects who discontinue from the study will complete the procedures for Visit 9 within 10 days of discontinuation (or as soon as possible after the site becomes aware of the discontinuation).

During the Extended Follow-up period, visits will be conducted via a telephone call at Week 27 (Visit 10) and at Week 38 (Visit 11). Visit 11 will be the end of study (EOS) visit.

The Sponsor will be unblinded after Week 16 (Visit 9), while the Sites and subjects will remain blinded until the end of the Extended Follow-up period at Week 38 (Visit 11). During the study, database will be locked twice; Week 16 (Visit 9) to assess safety and efficacy, and at Week 38 (Visit 11) to assess other outcomes during the Extended Follow-up period.

The study design schema is presented in.

[figure not shown]
[figure not shown]
[figure not shown]
[figure not shown]

Figure 1 Study design schema

# 3.3. Determination of Sample Size

Power analysis for sample size calculation was performed under 2-sample t-test at the 5% level of significance to identify significance of the difference between MT-2990 and placebo on the mean change from Baseline through Week 16 in nonmenstrual pelvic pain. A total of 28 subjects per arm will provide at least 80% power for detecting a clinically meaningful difference (placebo versus treatment) of -0.5 in the mean change from Baseline in nonmenstrual pelvic pain and a standard deviation (SD) of 0.65,

As this study is exploratory study (proof of concept study), multiplicity for multi-endpoint is not considered. Assuming a drop-out rate of 25%, a total of 76 subjects (38 subjects per arm) are planned to be randomized in this study.

# 4. PLANNED ANALYSIS

### 4.1. Interim Safety Assessment

There will be 3 interim safety assessments. The first interim assessment for safety will be performed when 20 subjects are randomized and have completed the Week 2 visit. The second interim assessment for safety will be performed when 50% of the subjects are randomized and have completed the Week 4 visit. The third interim assessment for safety will be performed when 50% of the subjects are randomized and have completed the Week 16 visit.

### 4.2. Final Analysis

Final data analysis will be conducted after database lock.

# 4.3. Data Monitoring Committee (DMC)

An independent DMC, composed of experts in the management of subjects with the disease under study will be established for MT-2990-A01 according US FDA guidance. An independent biostatistician will be assigned to the DMC to maintain the integrity of the study blind and provide safety data at regular predefined intervals during the study and provide the interim safety assessments to the DMC.

The primary purpose of this committee will be to review safety data for the protection of subject safety (including infusion site reactions, hypersensitivity and immune system disorders such as allergic reaction, anaphylaxis, cytokine release syndrome, etc).

There will be 3 interim safety assessments as described in section 4.1. The planned interim safety assessments will be conducted to determine whether the study will be stopped due to safety concerns.

A DMC charter will outline the scope and key responsibilities, timing of reviews, communications between the DMC and the Sponsor, and recommendations and action rules for

the study.

### 5. ANALYSIS POPULATIONS

The statistical analysis will be based on separate analysis sets, defined as follows:

- Randomized (RAND) population:
  - Will include all randomized subjects.
- Safety (SAF) population:
  - Will include all randomized subjects who received at least 1 dose of study medication.
- Intent-to-treat (ITT) population:
  - Will include all randomized subjects who received at least 1 dose of study medication and have at least 1 postscreening efficacy assessment.
- Per-protocol (PP) population:
  - Will include all ITT subjects who do not have any important protocol deviations and have completed the Double-blind Treatment period.
- Pharmacokinetics (PK) population:
  - Will include all randomized subjects who received at least 1 dose of MT-2990 and have at least 1 postdose value for serum concentration without important protocol deviations which may affect the PK of MT-2990.

• Pharmacodynamics (PD) population:

Will include all randomized subjects who receive at least 1 dose of study medication and had at least 1 post—dose PD assessment and for whom the PD data are considered to be sufficient and interpretable.

Important protocol deviations will be identified and documented during a data review prior to database lock and confirmed by database lock.

#### 6. STATISTICAL CONSIDERATIONS

### 6.1. Descriptive Statistics

### (1) Non-PK related

Continuous data will be summarized descriptively using the number in the analysis set (N), the number of observations (n), mean, standard deviation (SD), median, minimum and maximum. Categorical data will be summarized using frequency counts and percentages. The denominator for the percentages will be the total number of subjects in the treatment group or analysis population being presented, unless otherwise specified.

### (2) PK related

Serum concentrations will be summarized descriptively using N, n, mean, SD, median, minimum and maximum.

#### 6.2. Statistical Tests

Unless otherwise specified, all formal statistical tests of treatment effects will be done at two-sided significance level of 0.05. Point estimates will be accompanied with two-sided 95% confidence intervals where applicable.

#### 7. DATA CONVENTIONS

### 7.1. Analysis Variable Definitions

### 7.1.1. Study Subjects

### 7.1.1.1. Demographic and Other Baseline Characteristics

### (1) Age

Age will be calculated as the integer difference in years from date of birth to informed consent date.

# (2) BMI

BMI will be recalculated using the formula below and reported to 1dp. BMI  $(kg/m^2)$  = weight at Day 1 (kg) / {height (m)}

# (3) Years from initial diagnosis

Years from initial diagnosis will be derived from record of subject's medical history which has a value of "Endometriosis". Calculation will be done on a year part of the record as below.

Years from initial diagnosis = Year of first diagnosis of Endometriosis – Year of informed consent date

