8.3 Subject Inclusion Criteria

1. Subject must sign the written informed consent form (ICF) to participate in this study.

Inclusion Criteria for Entry into the Washout Period (if applicable [in addition to Inclusion Criteria 5 through 9]):

3. Subject agree to approximately 90-day washout interval of hormonal therapies, if applicable.

[figure not shown]
Inclusion Criteria for Entry into the Screening Period

- 4. Subject undergoing the Washout period (if applicable), must have a menstrual cycle with an interval of 21 to 38 days prior to entering the Screening period.
- 5. Subject must have a body mass index < 45 kg/m² (inclusive) at Screening and Day 1.
- 6. Subject who has documented surgical/laparoscopy diagnosis of endometriosis within 10 years of the Screening period.
- 8. Subject agrees to use 2 forms of nonhormonal contraception throughout the study (refer to Section 8.6.2).

9. In the Investigator's opinion, subject is able to understand the nature of the study and any risk involved in participation and is willing to cooperate and comply with the protocol restrictions and requirements including TVU.

Inclusion Criteria for entry into the Double-blind Treatment Period

11. Subject must have had 2 menstrual cycles with an interval of 21 to 38 days prior to treatment Day1.

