14.3.3 Analysis of Demography and other Screening Subject Characteristics

Demographic and other Screening variables include age, sex, height, weight, ethnic origin, medical history, and concomitant medication.

Age, sex, height, weight and ethnic origin will be summarized. Age will be calculated as the integer difference in years from date of birth to ICF date. Medical history and concomitant medications will be listed by subject.

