# 8.1.4. Demographic and Other Baseline Characteristics

The following demographic and other baseline characteristics will be used.

	Category	Descriptive
Age		Yes
Sex	Female	Yes
Ethnicity	Hispanic or Latino, Not Hispanic or Latino, Not Reported, Unknown	Yes
Race	American Indian or Alaska Native, Asian, Black or African American, Native Hawaiian or Other Pacific Islander, White, Not Reported, Other	Yes
Height (cm)		Yes
Weight at Day 1 (kg)		Yes
BMI (kg/m  )		Yes
Baseline nonmenstrual pelvic pain		Yes
Baseline dysmenorrhea		Yes
Baseline dyspareunia score		Yes

Usage of analgesic agents	
	Yes
Years from initial diagnosis	Yes

Demographic and other baseline characteristics will be summarized on the SAF and ITT population.

Demographic and other baseline characteristics will be listed on the RAND population. If several kinds of race are selected in the eCRF, it is treated as 'Multiple' in SDTM. Medical history will be summarized and listed on the SAF population.

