### 8.2.1. Primary Efficacy Endpoint

[figure not shown]
Mean change from Baseline through Week 16 in nonmenstrual pelvic pain will be analyzed in table.

As the Primary analysis, Change from Baseline through Weeks 4, 8, 12, and 16 in the mean scores of nonmenstrual pelvic pain will be analyzed using a repeated measures analysis of covariance model with an unstructured covariance structure. The analysis model will include Baseline value of the endpoint and baseline value\*treatment as a covariate; weeks, treatment and weeks\*treatment as fixed effect; subjects as random effect. The Kenward-Roger approximation was used to estimate the denominator degrees of freedom. Point estimates and 95% CIs for the difference between each active dose and placebo at Week 16 and other time points will be obtained. In the event that this analysis model fail to converge, ARH(1), AR(1), CS correlation matrix will be used sequentially.

The primary efficacy analysis will be also performed on PP population.

As the secondary analysis, the primary analysis will be conducted for the primary endpoint with the last observation carried forward method for imputing the missing value at or before the Week 4, 8, 12 and 16.

[figure not shown]

Time to rescue medications is defined as the number of days from Day 1 to the first use of a rescue medication during the treatment period for patients who did not take rescue medications in the last 35 calendar days during the screening period.

Time to rescue medications will be analyzed using a log-rank test, and significance difference test based on Restricted Mean Survival Time. Same analyses will be conducted for time to hospitalization and time to surgeries.

The logistic regression model will be used to analyze the response rate (percentage) based on nonmenstrual pelvic pain . Odds ratio and risk ratios for the percentage of responders will be calculated. The analysis model will include categorization of "response" and "no response" as the dependent variable, treatment arm as the main effect, and the Baseline score for nonmenstrual pelvic pain as the covariate. This analysis will be conducted using observed case and last observation carry forward (LOCF) respectively. The last observation carried forward method will be used for the missing value at or before Week 16.

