In addition, this analysis will be conducted to dysmenorrhea pain responders and dyspareunia pain responders in the same way. And, in each responder modified by analyses will be repeated in the same way.

The plot of LS mean of change from baseline value (and SE as error bar) of dysmenorrhea and dyspareunia score will be generated.

[figure not shown]
The plot of LS mean percentage change from baseline value (and SE as error bar) of dysmenorrhea and dyspareunia score will be generated.

The ROC curve of cutoff numbers for clinical responder based on nonmenstrual pelvic pain, dysmenorrhea and dyspareunia score scale will be generated.

Responder modified by analysis use analyses will also be performed by subgroups described as below. This subgroup analysis will be performed on Week 12 and Week 16 values.

Subgroup	Category
Age	$< 25, \ge 25 \ and \le 35, > 35$
Race	American Indian or Alaska Native, Asian, Black or African
	American, Native Hawaiian or Other Pacific Islander, White, Not

	Reported, Other	
Ethnicity	Hispanic or Latino, Not Hispanic or Latino, Not Reported,	
	Unknown	
Baseline pain score for	< Median of Baseline pain score for DYS	
DYS	≥ Median of Baseline pain score for DYS	
Baseline pain score for	< Median of Baseline pain score for NMPP	
NMPP	≥ Median of Baseline pain score for NMPP	
Baseline pain score for	< Median of Baseline pain score for dyspareunia	
dyspareunia	≥ Median of Baseline pain score for dyspareunia	
Baseline analgesic use		
Time since diagnosis	$< 2, \ge 2 \ and < 5, \ge 5$	

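### The SAP formula for years from initial diagnosis subtracts the wrong way round, so every eligible subject gets a zero or negative value

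*SAP*

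**What the plan says.** SAP section 7.1.1.1 (3) takes the endometriosis record from medical history, keeps only the calendar year, and defines the variable as "Year of first diagnosis of Endometriosis – Year of informed consent date".

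The variable is a row of the baseline table in SAP section 8.1.4 ("Years from initial diagnosis"), marked for descriptive statistics. The same section says "Demographic and other baseline characteristics will be summarized on the SAF and ITT" populations, and plans a listing on the randomized population.

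The subgroup table for the responder analyses in SAP section 8.2 has a row "Time since diagnosis" with three categories: below 2, from 2 to below 5, and 5 or more. It gives no unit and no reference to a derivation.

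On eligibility, criterion 6 in protocol section 8.3 requires a "documented surgical/laparoscopy diagnosis of endometriosis within 10 years of the Screening period".

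**The concern.** A duration since diagnosis should be the later date minus the earlier one. The SAP names the two years in the opposite order. An eligible subject already has a documented diagnosis at entry, so the formula cannot return a positive value in ordinary conduct.

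Three things are at stake:

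- **Baseline table.** The mean and median would print with the wrong sign, and the minimum and maximum would change places.
- **Subgroup analysis.** The cut-points for time since diagnosis are positive. If this variable feeds that row, the subgroup collapses to one level.
- **Traceability.** SAP section 1 says that its statistical details override those of the protocol, so this formula governs. A programmer who silently corrects it departs from the approved specification. A second programmer who follows the text would not reproduce the result.

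**Working it through.** The documents state no figure for this variable, so there is none to reproduce. The check is direct arithmetic on the formula.

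**Inputs**

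- Formula: diagnosis year minus consent year (SAP 7.1.1.1 (3)).
- Order of events: the qualifying diagnosis precedes Screening by at most 10 years (protocol 8.3, criterion 6). Where a Washout period applies, criteria 5 through 9 must also be met at entry to it.
- Subgroup cut-points: 2 and 5 (SAP section 8.2).

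**Step 1: sign.** Let g = consent year − diagnosis year, so g ≥ 0. The SAP formula returns −g and the reversed formula returns +g. With consent in 2019 as an example:

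| Diagnosis year | As written | Reversed |
|---|---|---|
| 2019 | 2019 − 2019 = 0 | 0 |
| 2016 | 2016 − 2019 = −3 | 3 |
| 2014 | 2014 − 2019 = −5 | 5 |
| 2009 | 2009 − 2019 = −10 | 10 |

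**Step 2: range.** For a qualifying diagnosis within 10 years, the values as written are 0, −1, …, −10. If the first medical-history record of endometriosis predates the qualifying surgical diagnosis, lower values are possible. A 2004 record with consent in 2019 gives 2004 − 2019 = −15. The sign does not change.

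**Step 3: intended direction.** The age rule in the same section says "Age will be calculated as the integer difference in years from date of birth to informed consent date", which runs from the earlier date to the later. Treatment duration in SAP 7.1.1.2 (1) subtracts the first dose date from the later date. The diagnosis formula is the odd one out.

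**Step 4: search for a correction.** No visible text takes an absolute value or restates the formula. SAP section 10, on changes from the protocol, does not mention it. Protocol section 14.3.3 gives no fallback definition, because its list does not contain the variable: "Demographic and other Screening variables include age, sex, height, weight, ethnic origin, medical history, and concomitant medication".

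**Step 5: subgroup, conditional.** Suppose that the subgroup row uses this variable in years. The 11 possible values from Step 2 then fall as follows:

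| Category | As written | Reversed |
|---|---|---|
| below 2 | 11 | 2 (0, 1) |
| 2 to below 5 | 0 | 3 (2, 3, 4) |
| 5 or more | 0 | 6 (5 to 10) |

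These are counts of possible values, not of subjects.

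**Step 6: primary analysis.** The covariates in SAP section 8.2.1 are "Baseline value of the endpoint and baseline value" by treatment, alongside week and treatment terms. Years from diagnosis does not enter.

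**The case against.** The strongest reply is that this is a transposition in one descriptive variable. The intent is plain from the variable's name, from the age rule and from the positive cut-points. A negative number of years would be noticed in the first draft table, and no data are lost. The variable enters neither the primary model nor the visible responder model, which uses treatment and baseline score. That stands, and it limits how serious the point is. It does not make the formula right.

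The second reply concerns the subgroup. The label differs from the variable name, no unit is given, and parts of the SAP are missing from the public version, so a definition could lie in text that cannot be seen. That also stands: the empty categories are a conditional consequence, and the request about the subgroup can only be for clarification.

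One could also read the dash as meaning from one year to the other. That does not stand, because the treatment duration formula that follows uses the same dash as a minus sign, with the later date first.

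A positive value would need a diagnosis year after the consent year. That could happen only if consent came before the diagnosis and a year-end fell between them. The entry criteria make this unlikely.

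**Conclusion.** The formula is wrong as written. In ordinary conduct every eligible subject gets zero or a negative value, from 0 to −10 for a first diagnosis within the 10-year window and lower if the first recorded diagnosis is older. The absolute value is correct throughout. The certain effect is a wrong sign in two planned baseline summaries and one listing.

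Confidence is high for the sign error. It is moderate for the subgroup effect, which assumes that the row uses this variable in years. If it does, that exploratory subgroup analysis tells the reader nothing. The primary efficacy conclusion does not depend on this variable.

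**What to change.** In SAP section 7.1.1.1 (3), reverse the subtraction: year of informed consent minus year of first diagnosis. Keep the calendar-year convention.

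In the subgroup table in SAP section 8.2, confirm whether time since diagnosis is this variable, and state the unit. If it is derived in another way, add or cross-reference that derivation.

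The cost is two short wording changes. No new data are needed, and no other visible analysis is affected.
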